10.5 INFORMED CONSENT

This study will be conducted in compliance with ICH E6 Good Clinical Practice: Consolidated Guidelines pertaining to informed consent. At the first visit, prior to initiation of any study-related procedures, patients must give their written consent to participate in the study after having been informed about the nature and purpose of the study, participation/termination conditions, and risks and benefits. The informed consent document must be signed and dated by the patient and PI, or designee, prior to study participation. A copy of the informed consent document must be provided to the subject. Signed consent forms must remain in the subject's study file and be available for verification by Sponsor or its representative at any time.

10.6 RECORDS

The results from Screening and data collected during the study will be recorded in the subject's eCRF. To maintain confidentiality, the subjects will be identified only by numbers and initials.

The completed eCRFs will be transferred to the Sponsor or designee. Copies of each eCRF will be retained by the PI. All source documents, records, and reports will be retained by the clinic.

All primary source data or copies thereof (e.g., laboratory records, eCRFs, data sheets, correspondence, photographs, and computer records) that are a result of the original observations and activities of the study and are necessary for the reconstruction and evaluation of any study report will be retained in the clinic archives.

Sponsor will inform the PI of the time period for retaining these records to comply with all applicable regulatory requirements. The minimum retention time will meet the strictest (longest) standard applicable to that site for the study, as dictated by any institutional requirements or local laws or regulations, or Sponsor standards/procedures; otherwise, the

retention period will default to the retention period of 15 years following completion of the clinical trial.

10.7 DATA MONITORING COMMITTEE

A Data Monitoring Committee (DMC) will be established in order to protect subject welfare, preserve study integrity, and provide recommendations as needed regarding study conduct. The DMC will be comprised of two external liver disease clinical experts as well as a statistician and a medical team member from the sponsor. The DMC will meet at predefined time points and on an as-needed basis based on enrollment, treatment milestones, and safety. Formal minutes and recommendations will be provided by the DMC to the sponsor regarding additional data requests and the continuation of the conduct of the study as outlined in the current protocol. The DMC will operate under the guidance of an agreed-upon charter.

Pain	Does not interfere with activity	Repeated use of non-narcotic pain reliever more than 24 hours or interferes with activity	Any use of narcotic pain reliever or prevents daily activity	Emergency room visit or hospitalization
Tenderness	Mild discomfort to touch	Discomfort with movement	Significant discomfort at rest	Emergency room visit or hospitalization
Erythema/Redness ^a	2.5–5 cm	5.1–10 cm	> 10 cm	Necrosis or exfoliative dermatitis
Induration/Swelling ^b	2.5–5 cm and does not interfere with activity	5.1–10 cm or interferes with activity	> 10 cm or prevents daily activity	Necrosis

Notes: The FDA Toxicity Grading Scale for Healthy Adult and Adolescent Volunteers enrolled in Preventive Vaccine Clinical Trials can be found at:

<http://www.fda.gov/BiologicsBloodVaccines/GuidanceComplianceRegulatoryInformation/Guidances/Vaccines/ucm074775.htm>.

^a In addition to grading the measured local reaction at the greatest single diameter, the measurements should be recorded as a continuous variable.

[figure not shown]
[figure not shown]
^b Induration or swelling should be evaluated and graded using the functional scale as well as the actual measurement.

APPENDIX B—NUMERIC RATING SCALE FOR ITCH AND FATIGUE

ITCH SEVERITY

Instructions:

Please clearly mark an 'x' in the box (☒) that best describes your **itching** in the **past 24 hours**.

APPENDIX C—5-D PRURITIS SCALE

5-D Pruritus Scale					
1. Duration : During the last 2 weeks, how many hours a day have you been itching?					
Less than 6hrs/day  1	6-12 hrs/day  2	12-18 hrs/day  3	18-23 hrs/day  4	All day  5	
2. Degree : Please rate the intensity of your itching over the past 2 weeks					
Not present  1	Mild  2	Moderate  3	Severe  4	Unbearable  5	
3. Direction : Over the past 2 weeks has your itching gotten better or worse compared to the previous month?					
Completely resolved  1	Much better, but still present  2	Little bit better, but still present  3	Unchanged  4	Getting worse  5	
4. Disability: Rate the impact of your itching on the following activities over the last 2 weeks					
Sleep	Never affects sleep  1	Occasionally delays falling asleep  2	Frequently delays falling asleep  3	Delays falling asleep and occasionally wakes me up at night  4	Delays falling asleep and frequently wakes me up at night  5
Leisure/Social	N/A 	Never affects this activity  1	Rarely affects this activity  2	Occasionally affects this activity  3	Frequently affects this activity  4
Housework/Errands		 1	 2	 3	 4
Work/School		 1	 2	 3	 4
5. Distribution: Mark whether itching has been present in the following parts of your body over the last 2 weeks. If a body part is not listed, choose the one that is closest anatomically.					
Head/Scalp Face Chest Abdomen Back Buttocks Thighs Lower legs Tops of Feet/Toes	Present        	Soles Palms Tops of Hands/Fingers Forearms Upper Arms Points of Contact w/ Clothing (e.g. waistband, undergarment) Groin	Present      		

APPENDIX D—MAYO PARTIAL IBD SCORE (INFLAMMATORY BOWEL DISEASE SCALE)

Components of the Partial Mayo Score

Stool Frequency

0 = Normal

1 = 1–2 stools/day more than normal

2 = 3–4 stools/day more than normal

3 = >4 stools/day more than normal

Rectal bleeding^a

0 = None

1 = Visible blood with stool less than half the time

2 = Visible blood with stool half of the time or more

3 = Passing blood alone

Physician rating of disease activity

0 = Normal

1 = Mild

2 = Moderate

3 = Severe

^a A score of 3 for bleeding required patients to have at least 50% of bowel motions accompanied by visible blood and at least one bowel motion with blood alone.

Primary Sclerosing Cholangitis (PSC), a chronic cholestatic liver disease, is characterized by inflammation and onion skin-layers of connective tissue around the biliary system, which finally leads to liver cirrhosis. Ongoing destruction to intra and/or extrahepatic bile ducts often leads to cholestasis, advanced fibrosis, liver cirrhosis, and eventually liver failure. The etiology to PSC is still not clear. It may be caused by multiple factors, such as autoimmunity, portal bacteremia, absorption of toxins, ischemic injury, viral infections, and toxic bile acids in the context of a genetic predisposition. PSC can be diagnosed via a complication, such as cholangitis or hepatic occurs.

There is not any established or approved pharmacologic therapy to PSC until now. The primary treatment to this disease is endoscopic/radiologic dilatation or stenting of bile-duct strictures to slow the progression of disease. Ursodeoxycholic acid (UDCA) is considered the only pharmacologic treatment option with significant biochemical response after multiple prospective clinical studies. However, patients with high PSC and high serum alkaline phosphatase (ALP) usually fail to respond to UDCA therapy. Although orthotopic liver transplantation is the only clinically proven treatment, PSC recurs in up to one-third of deceased donor liver transplantation and up to two-thirds of living-related donor liver transplantation patients.

FGF19 is an endocrine hormone secreted in the ileum and is considered to play an important role in the regulation of bile acid (BA), glucose, and lipid synthesis, as well as energy homeostasis in adult mammals. It has been proven that FGF19 mRNA expression and gall bladder levels are reduced in PSC patients in recent clinical data.

[REDACTED]

With previous clinical studies, treatment with NGM282 has been proven to have favorable safety and tolerability in normal volunteers and PBC patients. By pharmacologic FGF19 signaling to reduce the synthesis of toxic bile acids, NGM282 presents a great potential treatment to PSC. This statistical analysis plan is to describe the details of the interim statistical analysis parameters and methods for NGM's protocol 15-0106, Amendment 2, issued in 27May2016.

Objectives

1.1. Primary Objective

- Evaluate the treatment effect of NGM282 as measured by the mean change in ALP from Baseline to Week 12 in patients with PSC.

1.2. Secondary Objectives

Secondary objectives are to:

- Assess the safety and tolerability of NGM282 in patients with PSC with 12 weeks of treatment
- Evaluate the percentage change from Baseline at Week 12 in ALP
- Evaluate the absolute and percentage changes from Baseline at Week 12 in the following:

- ALT, AST, bilirubin (total, direct), and GGT
- Total cholesterol, HDL-cholesterol, LDL-cholesterol, and triglycerides
- Serum bile acids
- Bile-mediated absorption as measured by fat-soluble vitamins
- Compare the incidence and severity of IBD-associated intestinal symptoms
- Compare the incidence and severity of acute cholangitis during the study period.
- Evaluate the exposure of 1 mg and 3 mg of NGM282 in patients with PSC
- Compare the dose-related changes in safety, tolerability, and pharmacodynamic (PD) parameters

2. Investigational Plan

2.1. Overall Study Design and Plan

This is a multiple center, randomized, double-blind, placebo-controlled, parallel-group study of NGM282 when administered for 12 weeks as a daily subcutaneous (SC) injection in subjects with PSC. About 60 from the 90 screened subjects will be randomized to one of the three treatment arms (NGM282 1 mg, NGM282 3 mg, or Placebo) in a ratio of 1:1:1. Subjects will be assessed according to the schedule of procedures and assessments (Appendix 13.1).

2.2. Study Endpoints

The primary efficacy endpoint is defined as the mean change in ALP from Baseline at Week 12.

The secondary efficacy and PD endpoints are the following:

- Percent change from Baseline at Week 12 in ALP
- Changes and percent changes from Baseline at Week 12 in the following
 - ALT, AST, bilirubin (total, direct), and GGT
 - Total cholesterol, HDL-cholesterol, LDL-cholesterol, and triglycerides
 - Bile-mediated absorption as measured by fat-soluble vitamins
- Severity of IBD-associated intestinal symptoms

2.3. Treatments

Subjects will be instructed to self-administer/dose at approximately the same time each morning in the whole treatment period. Blinded study drug (NGM282 or placebo) will be administered as a subcutaneous (SC) injection in the abdomen. Subjects will be trained on self-administering a

SC injection. Self-administration will occur in clinic under the observation of clinic staff on weeks 1, 2, 4, 8, and 12.

3. General Statistical Considerations

Continuous data will be summarized using descriptive statistics (i.e. n, mean, standard deviation, median, minimum, and maximum). Categorical data will be summarized using the subject count and percentage in each category. For the summary statistics of all numerical variables, unless otherwise specified, minimum and maximum will be displayed to the same level of precision as the reported data. Mean and median will be displayed to one level of precision greater than the data collected. Standard deviation/standard error will be displayed to two levels of precision greater than the data collected. P-values will be rounded to three decimal places. If a p-value is less than 0.001 it will be reported as “<0.001.” If a p-value is greater than 0.999 it will be reported as “>0.999.”

Data will be displayed in all listings sorted by treatment group. Subjects will be identified in the listings by the subject identification number concatenated with the investigator number.

When count data are presented, the percentage will be suppressed when the count is zero in order to draw attention to the non-zero counts. The denominator for all percentages will be the number of subjects in that treatment within the analysis set of interest, unless otherwise specified.

Unless otherwise specified, Baseline will be defined as the last non-missing evaluation prior to or on the date of study drug SC injection (Day 1).

The study day will be calculated as follows:

If the assessment date occurs on or after the date of NGM282 SC injection (Day 1):

Study day = assessment date – date of NGM282 SC injection (Day 1) + 1.

If the date of interest occurs before the date of NGM282 SC injection (Day 1):

Study day = assessment date – date of NGM282 SC injection (Day 1)

[figure not shown]
There is no study day 0.

For all efficacy analyses, analysis visit windows will be used for assigning assessments to an analysis visit, as follows:

Scheduled Visit	Target Day	Visit Window (Days)
Screening	-42 to -1	Not applicable
Day 1	1	Not applicable
Week 1	7	4 to 10
Week 2	14	11 to 17
Week 4	28	25 to 31
Week 8	56	53 to 59
Week 12	84	81 to 87

Only those assessments which are assigned to an analysis visit will be included in the summary tables and figures which are presented by visit. For summaries of an event at or before a given time point, such as ALP at Week 12, all assessments (including unscheduled visits) on or before the upper limit of the corresponding visit window will be considered. If multiple assessments are assigned to an analysis visit, the nearest assessment to the target day will be defined as the primary analysis record for the summary analysis. All assessments will be presented in the data listings.

For tabulations of data on the Safety set, subjects who were randomized but did not receive treatment will not be included; however data for all subjects in the Safety set will be included in the data listings. In the listings, subjects who received treatment will be grouped by the actual treatment. Percentages for Safety set summaries will be based on the total number of subjects who receive treatment.

All analyses will be conducted using SAS Version 9.2 or higher.

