8.10.9 Interim Analysis

An unblinded interim analysis (IA) will be conducted when approximately 24 subjects (a minimum of 8 subjects per arm) have completed the Week 12 visit. At the IA, the evidence regarding the safety and efficacy of NGM282 in the PSC indication will be assessed, in order to evaluate the appropriateness of continuing the study.

A separate SAP for the IA will be generated, describing the conduct of the IA in detail.

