3.1. Sample Size

A sample size of 20 subjects randomized per treatment group was chosen in light of logistical needs and so as to accumulate sufficient safety data on NGM282. The associated power to detect a treatment difference in the primary efficacy analysis, for either NGM282 comparison versus placebo, is at least 90%, based on the following assumptions:

A. ALP Population Mean Change from Baseline:

	NGM282 (either 1 mg or 3 mg)		Placebo
Subjects taking UDCA at Baseline	-75	0	
Subjects not taking UDCA at Baseline	-475	0	

- B. Equal numbers of completing subjects for each of the four cells above
- C. Population (not sample) standard deviation (SD) between subjects within each of the four cells above: 200
- D. Analysis of variance with treatment, UDCA (yes/no), treatment with UDCA (all as classification variables), and Baseline value (as a continuous covariate) in the model
- E. 20% dropout rate, from randomization to Week 12, yielding 16 completing subjects per treatment group
- F. Dunnett's 1-step adjustment for multiplicity, requiring a type 1 error rate of 0.027 (2-sided) for each comparison versus placebo

Assumptions underlying the means and SDs are based on studies evaluating UDCA as a first-line therapy and in studies where secondary or combination therapies with UDCA have been utilized. The power in the primary efficacy analysis may be slightly higher, since it incorporates Dunnett's step-down adjustment and utilizes repeated measures to reduce the power losses due to dropouts. On the other hand, power may decrease slightly, to the degree that unequal numbers of subjects are randomized taking and not taking UDCA. In addition, the probability that the observed least square (LS) mean treatment difference exceeds 30% of the placebo LS mean change has not been examined.

To randomize 60 subjects, approximately 90 will be screened.

If, in contrast, the population SD is 300, the power is roughly 81% for each NGM282 comparison versus placebo.

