7.2. Secondary Efficacy Endpoint

The following endpoints will be analyzed for the FAS.

[figure not shown]
The endpoints among the following that are based on assessments scheduled for more than 1 post-treatment time point, will be analyzed using the FAS. They will be evaluated using MMRM analyses similar to that of the primary endpoint analysis. In contrast, the endpoints among the following based on assessments scheduled at Week 12 only will be evaluated using an ANCOVA model including treatment group, UDCA use, and treatment by UDCA use interaction as classification variables, and the Baseline value as the continuous covariate.

- Percent change from Baseline in ALP at Week 12
- Changes and percent changes from Baseline at Week 12 in the following:
 - ALT, AST, bilirubin (total, direct), and GGT
 - Total cholesterol, HDL cholesterol, LDL cholesterol, and triglycerides
 - Bile-mediated absorption as measured by fat-soluble vitamins

For each NGM282 treatment group, the LS mean rate (slope, per week) of change in ALP during weeks 1-4 will be compared to that during weeks 5-12. Changes in the slopes will be estimated with a MMRM from primary analysis. The same analysis will be done for percent change in ALP.

The relevance of the explanatory variables to each secondary efficacy endpoint will be checked. Similar to the model in the primary efficacy analysis, all relevant explanatory variables will be included into the analysis model with FAS.

The Mayo Partial IBD Score is a non-invasive 9-point partial Mayo score used as an outcome measure for clinical trials assessing therapy for ulcerative colitis. The Mayo Partial IBD Score will be assessed at all study visits. It is administered pre-dose at Day 1 and Weeks 1, 2, 4, 8, 12 and 16 (End of study). Severity of IBD-associate symptoms will be summarized with frequency and percentage.

8. Safety and Tolerability Analysis

Safety and tolerability will be assessed by clinical review and summaries of the following parameters:

1. AEs
2. Clinical laboratory test results
3. Physical examination results
4. LISSAs
5. Electrocardiogram results

6. Pregnancy Test
7. Vital signs

[figure not shown]
All safety and tolerability analyses will be conducted using the Safety Set. Percentage for the safety and tolerability analyses based on the number of subjects with a given event or attribute will be based on the number of subjects who were treated.

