8.5. Electrocardiogram

12-lead ECGs will be performed at Screening, Day 1, and weeks 12 and 16. ECG results are interpreted as Normal, Abnormal not clinically significant, or Abnormal clinically significant. This categorical data will be summarized in shift tables comparing the interpretations at each scheduled post-baseline visit with those at the Baseline visit.

Observed results at each visit will be presented in a listing.

[figure not shown]

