8.7. Local Injection-Site Symptom Assessments

The injection-site evaluation will be made using LISSA at Day 1, Weeks 1, 2, 4, 8, 12 and 16 (End of study). LISSA scores will be documented on the subject's eCRF.

A summary to the evaluated ISR will be presented with number and percentage of subjects at each time point by treatment group using Safety Set.

10. Data Monitoring Committee

A Data Monitoring Committee (DMC) will be established in order to protect subject welfare, preserve study integrity, and provide recommendations as needed regarding study conduct. The DMC will be comprised of two external liver disease clinical experts as well as a statistician and a medical team member from the sponsor. The DMC will meet at predefined time points and on an as-needed basis based on enrollment, treatment milestones, and safety. Formal minutes and recommendations will be provided by the DMC to the sponsor regarding additional data requests and the continuation of the conduct of the study as outlined in the current protocol. The DMC will operate under the guidance of an agreed-upon charter.

The analyses and outputs provided to the DMC are a subset of the IA and Full Study SAP.

11. Changes in the Planned Analysis

The descriptive summarization and MMRM ANCOVA model analyses for Change from Baseline in (5-D Pruritus Scale and Pruritus and Fatigue) were removed from the current SAP. At this time only the listings to display the data are planned.

The analyses for acute cholangitis were removed from the current SAP. At this time only the listings to display the data are planned.

The C4 and Serum bile acids, Fecal microbiome composition and PK data will not be transferred to [REDACTED] the Contract Research Organization performing the analyses of this SAP. Therefore, the analyses of these data were removed from this SAP.

12. References

Chuck Kincaid (2005). Guidelines for Selecting the Covariance Structure in Mixed Model Analysis, Proceeding of the 30th SAS Users Group International Conference.

Hollander, Myles, Douglas A. Wolfe. (1973),*Nonparametric Statistical Methods*, New York: John Wiley & Sons, 75-82.

Liu, H. (2007) Cochran-Armitage Trend Test Using SAS, *PharmaSUG 2007*, SP05.

13. Appendices

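### By-visit safety percentages are divided by all subjects in the arm, not by those assessed at the visit, so they shrink as assessments go missing

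*SAP*

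**What the plan says.** The general rule in SAP section 3 is "The denominator for all percentages will be the number of subjects in that treatment within the analysis set of interest, unless otherwise specified". The same section adds, for safety, "Percentages for Safety set summaries will be based on the total number of subjects who receive treatment", and the opening of SAP section 8 says again that such percentages "will be based on the number of subjects who were treated".

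Three safety summaries are by visit:
- **Injection-site reactions (8.7):** "presented with number and percentage of subjects at each time point by treatment group using Safety Set".
- **ECG (8.5):** "This categorical data will be summarized in shift tables comparing the interpretations at each scheduled post-baseline visit". ECGs after Day 1 are taken only at Weeks 12 and 16.
- **Laboratory values (8.2):** shift tables from Baseline to each scheduled post-baseline visit.

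Sections 8.2 and 8.5 do not mention percentages themselves, but section 3 does for all such data: "Categorical data will be summarized using the subject count and percentage in each category". None of the three sections names a different denominator or provides a row for subjects not assessed. Elsewhere the SAP does name one where it wants to, as in 4.1 (disposition), 6.2.2 (compliance) and 8.1.5 (withdrawals). The silence in 8.2, 8.5 and 8.7 therefore leaves the default in force.

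**The concern.** Dividing by all treated subjects suits a question such as whether a subject ever had a TEAE. It does not suit a status that can be seen only in subjects examined at a particular visit. Protocol 5.9.9 describes the injection-site assessment as a picture of the site at the clinic visit, not a record of what happened between visits. A subject with no Week 12 assessment cannot be in the Week 12 numerator but remains in the denominator.

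Two consequences follow. Rates drift downward at later visits for a reason unrelated to the drug. And if more assessments are missing in an active arm than on placebo, that arm's percentages are lowered more, so a tolerability difference can be hidden or reversed on the page. This SAP describes the interim analysis, where the appropriateness of continuing is judged (Protocol 8.10.9), and the outputs given to the DMC are drawn from it and from the full-study SAP (SAP section 10).

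**Working it through.** **Inputs.** From SAP 3.1: 20 randomized per arm and "20% dropout rate, from randomization to Week 12, yielding 16 completing subjects per treatment group". From Protocol 8.10.9: "An unblinded interim analysis (IA) will be conducted when approximately 24 subjects (a minimum of 8 subjects per arm) have completed the Week 12 visit". All event rates, unequal missingness and numbers dosed at the interim used below are assumptions for illustration.

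**Plan's own figure.** 20 × (1 − 0.20) = 16 per arm. This reproduces.

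**Formula.** Let r be the rate among subjects assessed at the visit, m the number assessed and N the number in the set. The SAP rule prints r × m / N, so the factor is m / N.

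**1. Range at Week 12, final analysis.**
- All 20 assessed: 20/20 = 1.00.
- No dropout assessed: 16/20 = 0.80. A 40% rate prints as 0.40 × 0.80 = 32%. Four reactions print as 4/20 = 20% instead of 4/16 = 25%.

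**2. Shift table, same case.** Suppose 16 of 20 have both a Baseline and a Week 12 ECG, 12 normal and 4 abnormal at Week 12. The rule prints 12/20 = 60% and 4/20 = 20%, which sum to 80%. On assessed subjects the figures are 12/16 = 75% and 4/16 = 25%, which sum to 100%.

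**3. Unequal missingness.** Assume 30% missing on active (14 of 20 assessed) and 10% on placebo (18 of 20).
- 40% among those assessed in both arms: 0.40 × 14/20 = 28% against 0.40 × 18/20 = 36%, a difference of 8 points in favour of active that the assessed data do not show.
- 50% against 40% among those assessed: 0.50 × 14/20 = 35% against 36%. A 10-point excess disappears.

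**4. Interim.** Take 8 per arm with Week 12 done and an assumed 8 to 20 dosed per arm in the data cut.
- 8 dosed: 8/8 = 1.00.
- 12 dosed: 8/12 = 0.67.
- 20 dosed: 8/20 = 0.40.

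Two reactions among 8 assessed (25%) would print as 25%, 2/12 = 16.7% and 2/20 = 10% respectively.

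**The case against.** The strongest reply is that the documents provide for assessing subjects who leave early. The schedule has one shared column for Week 12 and Early Withdrawal, with injection-site, ECG and chemistry assessments marked. Protocol 5.6.7 lists those procedures and a 4-week follow-up for early-withdrawal subjects, and Protocol 5.4 calls for efforts to obtain the final Week 12 and Week 16 assessments. The narrow visit windows in SAP section 3 are stated for efficacy analyses, so early-withdrawal records may well appear under Week 12 in safety tables. The 20% is a dropout assumption for the power calculation, not a rate of missing safety assessments. All of this stands: 0.80 is the figure if no dropout is assessed, not the expected one.

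It is also fair that changing the denominator does not recover reactions in subjects who left because of them. If 10 of 20 would react and 6 of those leave unassessed, the rule prints 4/20 = 20% and the change prints 4/14 = 29%; both fall well short of 50%. Such losses are better seen in the TEAE tables (8.1.1), the withdrawal table (8.1.5) and the discontinuation reasons (4.1).

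Finally, these are descriptive tables with no test attached, counts appear beside percentages, and all assessments are listed. That limits the importance of the point. It does not make the stated denominator right, and nothing in the rule requires the number assessed to be shown.

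**Conclusion.** The point holds for injection-site reactions, ECG shifts and laboratory shifts by visit. Followed as written, the SAP prints percentages diluted by the factor n assessed / n in the set: between 1.00 and 0.80 at Week 12 under the planned dropout, with distortion between arms if missingness is unequal. The primary MMRM, overall TEAE incidence and TEAEs leading to withdrawal are not touched.

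Four stronger readings are tempting and are not supported:
- **That unassessed subjects count as event-free in every by-visit table.** This is the arithmetic effect in a present/absent table such as injection-site reactions. In a shift table they fall in no category, so normal is understated along with abnormal and the shortfall from 100% is visible.
- **That every Week 12 percentage will be 0.80 of the true figure.** That requires that no dropout has an early-withdrawal or final assessment.
- **That the interim tables will be understated by some stated amount.** The factor could go below 0.80 if treated subjects who have not reached the visit are in the data cut. The text available for review does not give the cut, and if only Week 12 completers are included the factor is about 1.00.
- **That Mayo severity is affected in the same way.** SAP 7.2 asks for frequency and percentage but does not say by visit; that display is only inferred from the assessment schedule.

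**What to change.** Keep the rules in SAP sections 3 and 8 for ever/never summaries, such as any TEAE or disposition. Add for by-visit categorical tables: *For injection-site reactions, ECG shifts and laboratory shifts (and Mayo severity, if shown by visit), the denominator is the number of subjects in the arm with a non-missing assessment at that visit; for shift tables, at both Baseline and that visit. This number is printed for each arm and visit, and subjects not assessed are shown in a separate row.*

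The cost is two sentences in the SAP and a change to the table programs; no new data are needed. The downside is that later percentages rest on smaller numbers and describe only subjects still being assessed. They do not correct for dropout caused by poor tolerability, so they should be read with the TEAE and discontinuation tables.
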